	
Inclusion criteria:
 
 • Men aged 18 years or older; • With a recorded diagnosis for any of the following, prior to index date: GERD, gastric and duodenal ulcers, chronic gastroduodenitis, Zollinger-Elison syndrome, OR with a recorded recent history of comedication with any of the following: NSAIDs, acetyl salicylic and derivatives, glucocorticoids, or antithrombotic treatments; • With at least one year of recorded medical history prior index-date. 
Exclusion criteria:
 
 • Those with recorded prescription of any PPIs or H2RAs within one year before index-date; • Those with recorded history of SD OR treatment for SD at any time prior index-date; • Those with recorded history of selected severe central nervous system comorbidities (Section 4.3, Table 1) prior to index-date; • Those with history of Helicobacter pylori (H. pylori) infection or use of fixed PPI-antibiotic treatments for this indication.
Treatment protocols	
Initiate any of the following substances (or none of them in the “non-initiators” cohort) at index-date (see definition below), as monotherapy (i.e., not in combination with another PPI or H2RA).
 
Target arms:
 
 • esomeprazole (target arm [Cohort 1]) • omeprazole (target arm [Cohort 2]) 
Comparator arms:
 
 • pantoprazole (comparator arm [Cohort 3]) in the IQVIA™ Disease Analyser (DA) Germany database) • lansoprazole (comparator arm [Cohort 4]) in the IQVIA™ Medical Research Data (IMRD) UK database) • H2RAs, all combined (comparator arm [Cohort 5]) • non-initiators of either PPIs or H2RAs (comparator arm [Cohort 6])
Assignment procedures	
We will assume treatments are randomly assigned within levels of the covariates identified as potential confounders [see Section 4.6, Potential confounding factors]

Index-date (cohort entry, beginning of follow-up)	
Active treatment arms (including PPIs and H2RAs [Cohort 1 to 5]): The index date will be the date of the initiation of treatment defined as a prescription date for PPIs/H2RAs after a washout window of at least 365 days in which no previous prescription with any PPIs or H2RAs have been recorded.
 
Non-initiator arm [Cohort 6]: Non-initiator comparators will be selected on each date of the recruitment period when esomeprazole/omeprazole initiators start treatment,

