 160 ^e Censoring: Patients will be censored at the earliest of the following events: first occurrence of outcome, loss to
 161 follow-up (e.g., transfer out date from the general practice in IMRD or end of continuous observation of the patient
 162 by the practice in IQVIA™ DA Germany, or date of last data collection from the practice), death (only available in
 163 IMRD UK), end of follow-up (1 year) or end of the study period.
 164

165 4.2. Data sources

166 The following databases will be used: IQVIA™ Disease Analyser (DA) Germany, and IQVIA™ Medical
 167 Research Data (IMRD) UK. Brief descriptions of these databases are provided in **Annex 1**.

168

169 4.3. Study population

170 The population eligible for the study will be selected based on the inclusion and exclusion criteria listed
 171 in Table 1, which will be measured at baseline (i.e., index-date). Figure 1 above provides details on the
 172 assessment windows for these eligibility criteria in relation to the index-date.

173 **Table 1.** Eligibility criteria.

Inclusion criteria	Exclusion criteria

 Patients registered with a general practice (GP) covered by IMRD or patients visiting GP in IQVIA™ DA Germany; 	
 Recorded prescription of any PPIs or H2RAs within one year before index-date;

 Male; 
AND
 
 Aged ≥18 years; 	
 Recorded history of SD OR treatment for SD (e.g., Viagra) prior index-date;

 At least one year of recorded medical history prior to index-date. 	
 Those with recorded history of selected severe CNS diseases prior index-date, namely: Hereditary ataxia (mainly hereditary spastic paraplegia), Huntington disease, spinal muscular atrophy and related syndromes, cerebral palsy, hemiplegia, paraplegia and tetraplegia, other paralytic syndromes (monoplegia of lower limb, cauda equina syndrome, locked-in syndrome), dependence on wheelchair.

 Recorded diagnosis for GERD, gastric and duodenal ulcers, chronic gastroduodenitis, and Zollinger-Ellison syndrome¹; 
OR
	--

Inclusion criteria	Exclusion criteria

 History of comedication with NSAID, acetyl salicylic and derivatives, glucocorticoids, and antithrombotic treatments ^{1, 2} 	

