 233 exposure) with any certainty. Electronic health records may not capture the entire patient
 234 history of utilisation of these treatments. In addition, these treatments are used
 235 interchangeably which would mean that a substantial number of individuals would be excluded
 236 from the study population if the study focuses only on first use ever of any of these
 237 substances. Therefore, the study will assess initiation of treatment after a washout window of
 238 at least 365 days.

239 Prescriptions will be identified through keyword searches using international non-proprietary
 240 names (INNs) in several prescription-related variables (e.g., "Therapy Name", "Product Name",
 241 "Molecule"). Detailed list of keywords used are provided in **Annex 2**.

242 PPIs will include the most prescribed substances in each database, i.e., esomeprazole,
 243 omeprazole, and pantoprazole in IQVIA™ DA Germany, and esomeprazole, omeprazole, and
 244 lansoprazole in IMRD UK. Other PPIs such as dexlansoprazole and rabeprazole are less
 245 commonly recorded in the selected databases and, therefore, will not be included in this study.

246 Products containing H2RAs will include the following substances (ordered by frequency of
 247 prescribing): ranitidine, famotidine, nizatidine, cimetidine in IMRD, and ranitidine, famotidine,
 248 cimetidine, nizatidine in IQVIA™ DA Germany.

249 **Annex 2** provides details on the use of PPI and H2RA substances over time in each database.

250

251 b) Non-initiators arm (cohort)

252 Non-initiator comparators will be randomly sampled and selected on each date of the
 253 recruitment period when esomeprazole/omeprazole initiators start treatment, **matched on**
 254 **birth-year**. This date will be the non-initiator comparators index-date. Thus, with regards to
 255 treatment, the active arms initiate a treatment on index-date and non-initiator comparators do
 256 not. Matching on index-date and on year of birth is meant to ensure a similar distribution of
 257 calendar time and age at index-date, both of which are considered important potential
 258 confounders.

259 It should be noted that *non-initiators* refer to patients who have selected indications (see Table
 260 1 above, inclusion criteria) recorded in the databases but who did not initiate therapy (i.e., did
 261 not have a recorded PPIs or H2RA prescription within 12 months before index-date or on index
 262 date).

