589 hospitalizations, and tests.

590

591

592

593

594

595 **Annex 2 - Codelists**

596

597 **EXPOSURES: PPIs AND H2RAs**

598

- 599 ○ **IQVIA™ Disease Analyzer Germany**

600 *PPIs*

INN	EPHMRA ATC Code	EPHMRA ATC Text
ACETYLSALICYLIC ACID + ESOMEPRAZOLE	B01C5	Platelet aggregation inhibitors, combinations
AMOXICILLIN + OMEPRAZOLE + CLARITHROMYCIN	A02B2	Proton pump inhibitors
DICLOFENAC + OMEPRAZOLE	M01A1	Anti-rheumatics, non-steroidal plain
ESOMEPRAZOLE	A02B2	Proton pump inhibitors
LANSOPRAZOLE	A02B2	Proton pump inhibitors
NAPROXEN + ESOMEPRAZOLE	M01A1	Anti-rheumatics, non-steroidal plain
OMEPRAZOLE	A02B2	Proton pump inhibitors
PANTOPRAZOLE	A02B2	Proton pump inhibitors

601

602 *H2ARs*

INN	EPHMRA ATC Code	EPHMRA ATC Text
CIMETIDINE	A02B1	H2 antagonist
FAMOTIDINE	A02B1	H2 antagonist
NIZATIDINE	A02B1	H2 antagonist
RANITIDINE	A02B1	H2 antagonist

603

604

- 605 ○ **IQVIA™ Medical Research Data (IMRD) UK**

606 *PPIs*

Generic Drug Name
ESOMEPRAZOLE
LANSOPRAZOLE
OMEPRAZOLE
PANTOPRAZOLE
RABEPRAZOLE
KETOPROFEN/OMEPRAZOLE
NAPROXEN/ESOMEPRAZOLE
AMOXICILLIN/CLARITHROMYCIN/LANSOPRAZOLE
METRONIDAZOLE/CLARITHROMYCIN/LANSOPRAZOLE

607 H2ARs

Generic Drug Name
CIMETIDINE
FAMOTIDINE
NIZATIDINE
RANITIDINE
RANITIDINE BISMUTH CITRATE
CIMETIDINE/ALGINIC ACID
FAMOTIDINE/CALCIUM/MAGNESIUM

608

609

610 **OUTCOME: SEXUAL DYSFUNCTION**

611

612 ○ **IQVIA™ Disease Analyzer Germany**

613

WHO ICD10 code	WHO ICD10 Text
F52.0	Lack or loss of sexual desire
F52.1	Sexual aversion and lack of sexual enjoyment
F52.2	Failure of genital response
F52.3	Orgasmic dysfunction
F52.6	Nonorganic dyspareunia
F52.8	Other sexual dysfunction, not caused by organic disorder or disease
F52.9	Unspecified sexual dysfunction, not caused by organic disorder or disease
N48.4	Impotence of organic origin
N94.1	Dyspareunia
N48.3	Priapism -- Painful erection

614

615 ○ **IQVIA™ Medical Research Data (IMRD) UK**

Read code	Term
E2275	Inhibited male orgasm
67IA	Advice about impotence
7A6G0	Revascularisation for impotence
7A6G5	Ligation of penile veins for impotence
Eu521	Sexual aversion disorder
K27y1	Impotence of organic origin
1ABG	Sexual intercourse difficult
1ABB	Cannot get an erection
1ABC	Cannot sustain an erection
ZV417	Abnormal sexual function
15D	Pain on sexual intercourse
E2273	Impotence
E2273-1	Erectile dysfunction

Read code	Term
Eu520-3	[X] Lack of libido
Eu521-1	[X]Anhedonia sexual
7C25E	Management of erectile dysfunction
Eu522	Failure of genital response

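### Table 1 omits the H. pylori and fixed-pack exclusion stated in Box 2, and the Annex 2 lists neither mark the packs as exclusion-only nor cover every PPI the washout refers to

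*Protocol*

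**What the plan says.** **Eligibility.** Section 4.3 makes Table 1 the selecting list: "The population eligible for the study will be selected based on the inclusion and exclusion criteria listed" there. The exclusions in Table 1 are a PPI or H2RA prescription in the prior year, a history of sexual dysfunction or its treatment, and severe CNS disease ("Those with recorded history of selected severe CNS diseases prior index-date, namely"). The remaining exclusion cell holds only a dash. Box 2, which summarises the methods, has the same three and a fourth: "Those with history of Helicobacter pylori (H. pylori) infection or use of fixed PPI-antibiotic treatments for this indication".

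**Washout.** Box 2 and Table 1 agree. Box 2 reads "Those with recorded prescription of any PPIs or H2RAs within one year before index-date" and Table 1 reads "Recorded prescription of any PPIs or H2RAs within one year before index-date". Section 4.6 defines non-initiators by the absence of any such prescription in the prior 12 months or on the index date. Section 4.7.4 opens the per-protocol analysis by censoring at the start of a PPI or H2RA other than the baseline one.

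**Codes.** Section 4.6 finds prescriptions by searching substance names and refers to Annex 2: "Detailed list of keywords used are provided in" that annex. Under its exposures heading, the German PPI list includes "AMOXICILLIN + OMEPRAZOLE + CLARITHROMYCIN", and the UK list includes two lansoprazole-antibiotic packs. Rabeprazole is on the UK list only; dexlansoprazole is on neither. Section 4.6 says of these two: "Other PPIs such as dexlansoprazole and rabeprazole are less" commonly recorded in the selected databases, and gives this as the reason for not studying them.

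**The concern.** Two programmers could build different cohorts from this Protocol. One who follows Box 2 removes men with an H. pylori history and users of fixed PPI-antibiotic packs. One who follows Table 1, the list that Section 4.3 designates, keeps both groups. Men with an H. pylori history could then enter any of the cohorts, including the non-initiators. Pack users could enter the arm named by the PPI in the pack: omeprazole, a target drug, in Germany, and lansoprazole, a comparator, in the UK.

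The second gap concerns what counts as any PPI. If German rabeprazole prescriptions exist but are not searched for, a man taking rabeprazole in the prior year can count as a new initiator of a study drug, or as an untreated non-initiator. The non-initiators are the group meant to show background risk. In the per-protocol analysis, a switch to rabeprazole would not be seen as a switch. The same applies to dexlansoprazole in either database.

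**Working it through.** The Protocol gives no figure to reproduce on this point: it sets no sample size, and recording frequencies are available only on request. The check compares texts and counts list entries.

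**1. Exclusions, Box 2 against Table 1**

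| Exclusion | Box 2 | Table 1 |
|---|---|---|
| PPI or H2RA in prior year | yes | yes |
| Prior sexual dysfunction or treatment for it | yes | yes |
| Severe CNS disease | yes | yes |
| H. pylori history or fixed PPI-antibiotic use | yes | no |
| Total | 4 | 3 |

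The notes to Figure 1 do not mention H. pylori either. The figure itself is not available to this review.

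**2. Annex 2 PPI lists**

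| | Germany | UK |
|---|---|---|
| PPI entries | 8 | 9 |
| of which PPI-antibiotic packs | 1 (omeprazole) | 2 (lansoprazole) |
| Rabeprazole | 0 | 1 |
| Dexlansoprazole | 0 | 0 |
| Single-substance entries that are not a study arm there | lansoprazole | pantoprazole, rabeprazole |

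The last row shows that the lists do more than define arms. They hold drugs that can only serve the washout or the censoring. No entry is labelled by purpose.

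**3. Would another rule remove pack users?** The monotherapy rule in Section 4.6 bars starting more than one PPI or H2RA on the same day, and it allows combinations with other kinds of drug. A pack holds one PPI plus antibiotics, so the rule lets it through. Of the rules shown, only the fourth exclusion in Box 2 bars a first pack prescription, and Table 1 lacks it.

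**4. Does the German list implement the any-PPI washout?** It holds esomeprazole, omeprazole, pantoprazole, lansoprazole and combinations of the first two. Section 4.6 excuses the absence of rabeprazole and dexlansoprazole as study drugs. It gives no reason to ignore them in the washout, and the UK list keeps rabeprazole although it is not studied there. On the printed list, the German washout therefore covers the listed PPIs, not any PPI.

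**5. Per-protocol censoring.** The opening sentence of that analysis in Section 4.7.4 covers any other PPI or H2RA. A later paragraph speaks of moving to an alternative arm and adds the end of the index treatment. The end-of-treatment event might catch some switches, but Section 4.9 says actual treatment duration is not available. Under the opening sentence, a switch to an unlisted PPI should censor, and the code list could not detect it.

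**The case against.** Box 2 is current text and states the exclusion in full, so the Protocol does not lack it. What is wrong is a contradiction with Table 1, and the consequence arises only if an analyst follows Table 1 alone. That is right. But Section 4.3 names Table 1 as the selecting list, and Box 2 itself points to Table 1 for its CNS exclusion, so following Table 1 is a natural course.

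A reader might infer that Annex 2 makes eradication packs study exposures. The documents do not support that as a fact. The same lists hold drugs that cannot be arms, and pack codes have to be listed somewhere for the Box 2 exclusion and the washout to be applied. Their presence is equally consistent with correct use. What stands is that nothing marks them as exclusion-only and that, without the Box 2 exclusion, nothing keeps them out of an arm.

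The German list may lack rabeprazole because none is recorded there. The search is by substance name across several fields, and an Excel version of the annex is not available to this review. This cannot be ruled out. Section 4.6, however, describes both drugs as less common in the selected databases, with no breakdown by database and no statement that either is absent.

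Detailed code lists are often left to a programming specification. Here the Protocol prints them and refers to them for the search, so they should agree with its own rules.

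**Conclusion.** The point holds as two inconsistencies to be corrected before data extraction: an eligibility contradiction between Box 2 and Table 1, made worse by unlabelled pack codes, and printed code lists narrower than the any-PPI wording of the washout and the per-protocol censoring. Both change who enters the cohorts, and the second also changes who is censored.

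The size is unknown and may be small. The Protocol gives no count of pack users, of men with an H. pylori history, or of rabeprazole or dexlansoprazole prescriptions in either database.

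A reader might want to express the problem as a stated dilution of the hazard ratio. The documents do not support one. It would need an assumed share of affected men and an assumption that wrongly included initiators carry no drug effect. German pack users are in fact prescribed omeprazole, and a former rabeprazole user who starts a study drug is also exposed. Nor do the documents support a claim that replication between databases fails: no replication criterion is stated, and the PPI comparators already differ by database by design.

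The conclusion assumes that the printed Annex 2 lists are the ones used, and that the unseen Figure 1 and Excel annex do not already resolve the matter.

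**What to change.** 1. Add the H. pylori / fixed PPI-antibiotic exclusion to Table 1 so that it matches Box 2.
2. In Annex 2, mark the three pack entries (one German, two UK) as exclusion and washout codes that do not define an arm.
3. Extend the list used for washout and per-protocol censoring to every PPI and H2RA recorded in each database: rabeprazole in Germany, and dexlansoprazole in both, if recorded. If a drug has no records in a database, say so in the annex.

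The cost is an edit to one table and the code lists before extraction. The cohort becomes slightly smaller than one built on Table 1 and the printed lists. For the H. pylori and pack users this is no loss against the plan, because Box 2 already excludes them.

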204 treatment episodes. Of note, eligibility criteria will be evaluated at each index-date every time the
205 patient contributes with a treatment episode. Figure 2 illustrates examples of patient exposure to
206 treatments for four different patients according to calendar time (in months).

[1] [Ranitidine-containing medicinal products - referral | European Medicines Agency \(europa.eu\)](https://www.ema.europa.eu/en/medicines/human/CTX/ranitidine)

207 **Figure 2.** Patient exposure to treatments according to calendar time.

208 Patient 1: Patient contributes with 1 treatment episode (first episode). The second episode does not meet the
 209 criterion of 1 year washout before index date.

210 Patient 2: Patient contributes with 1 treatment episode (first episode). The second episode does not meet the
 211 criterion of 1 year washout before index date.

212 Patient 3: Patient contributes with 2 treatment episodes. The second episode meets the criterion of 1 year washout
 213 before index date.

214 Patient 4: Patient contributes with 2 treatment episodes. The second episode meets the criterion of 1 year washout
 215 before index date.

216 The follow-up period illustrated here corresponds to the 12-month follow-up for the ITT analysis.

217 4.6. Variables

218 Exposure

219 a) Active treatment arm (cohorts):

220 Patients who **initiate treatment** with either target treatments (esomeprazole or omeprazole)
 221 or active comparators (pantoprazole, lansoprazole, H2RAs) during the study period will be
 222 identified based on the dates of prescriptions in the database and considering a washout period
 223 (See Figure 2 above) of 1 year before index-date in which no previous prescription with any
 224 PPIs or H2RAs have been recorded.

225 Only initiation of target treatments and active comparators as **monotherapy** will be included
 226 in the study. Initiating treatment with more than one PPI or H2RA or any combination of the
 227 two on the same day will be not allowed. However, combinations with treatments other than
 228 PPIs and H2RAs are allowed (e.g., alginates and antacid basic salts). Table 2 shows the
 229 treatment assignment by target/comparator arm.

230 Of note, considering that these treatments have been long available on the market, their
 231 prescribing pattern (on-demand or intermittent use) and widespread over-the-counter (OTC)
 232 use, it will not be possible to identify the first prescription ever (i.e., first use or incident

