417 another treatment was initiated. It should be noted that, in the analysis comparing with non-initiators,
418 we restricted the study population to patients with chronic indications, for which treatment is likely
419 chronic.

420 To our knowledge, the accuracy of diagnostic coding for sexual dysfunction has not been assessed in the
421 primary care databases available. However, the nature of the diagnosis means that its recording in
422 primary care records could be reasonably accurate, particularly for sexual dysfunction in male individuals.
423 Nonetheless, this assumption should be treated cautiously. In the UK, the patent for Viagra expired in
424 June 2013, which followed a drop by 93% in the price of generic preparations of sildenafil compared to
425 the price of branded Viagra (Connelly, 2017). Besides, Sildenafil has been available OTC without
426 prescription from UK pharmacies since 2017 and, therefore, patients have no longer needed to see their
427 doctor to get a diagnosis ever since. (MHRA, 2017) These events led to marked changes in diagnosis
428 coding practices of erectile dysfunction during 2013-2014 and marked decrease of coding for impotence
429 by GPs since 2017 which are reflected in the distribution of outcome events over calendar time. In
430 IQVIA™ DA Germany the reporting of male sexual dysfunction appears stable after 2005. To account for
431 uncertainties around potential misclassification due to changes in diagnostic criteria or coding practices
432 over time, calendar period will be adjusted for in the analysis.

433 It also needs to be considered that patient's medical history, as captured by GP practices included in
434 the study, may be incomplete, particularly in the IQVIA DA Germany database. In Germany, there is
435 no mandatory GP system and patients have free doctor choice. A specialist can be consulted without
436 referral from the GP. As a result, data are collected from visits to various medical practices which are
437 not linked by a unique patient identifier. Therefore, the entire medical history of patients might be
438 fragmented and for that reason there is a risk of exposure, outcome and covariates misclassification.
439 However, this misclassification will affect both target and comparator groups.

440 Although confounding by indication represents a common source of bias, it is not likely that the main

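### In DA Germany the look-back rule does not require that a man was observed at the practice during the 365-day washout, and the remark that both groups are affected is no safeguard because the error differs by arm

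*Protocol*

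**What the plan says.** Section 4.3, Table 1, sets one look-back rule for both databases: "At least one year of recorded medical history prior to index-date". The washout is an exclusion for "Recorded prescription of any PPIs or H2RAs within one year before index-date". The population basis differs by country: "Patients registered with a general practice (GP) covered by IMRD or patients visiting GP in IQVIA™ DA Germany".

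Section 4.6 defines both kinds of cohort by what the record lacks. Initiators are "identified based on the dates of prescriptions in the database and considering a washout period" of one year. Non-initiators (Cohort 6) are men with an indication who did "not have a recorded PPIs or H2RA prescription within 12 months before index-date or on index" date. They are sampled at random on dates when esomeprazole or omeprazole initiators start, matched on birth year.

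For Germany, sections 4.5 and 4.7.3 use "end of continuous observation of the patient" by the practice as a reason to stop follow-up. It is not used to qualify the look-back.

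Section 4.9 states that Germany has "no mandatory GP system and patients have free doctor choice", that specialists can be seen without referral, and that practices are not linked by a patient identifier. It accepts a risk of exposure, outcome and covariate misclassification and closes with: "However, this misclassification will affect both target and comparator groups".

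**The concern.** The 365-day washout is what makes this a new-user design, and the absence of a record is what defines Cohort 6. In the UK, registration with a practice gives that absence some meaning. In Germany, on the protocol's own description, a man can be away from the practice for the whole year, or be treated at another one, and his record will look the same as that of an untreated man.

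The consequence differs by arm. A missed prescription turns a continuing user into an apparent initiator in Cohorts 1 to 5, but a treated man into an apparently untreated one in Cohort 6. Cohort 6 is there to supply the background risk, because the active comparators may themselves carry the effect. In a study of a safety signal, dilution toward no difference is not a cautious error.

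**Working it through.** **Does the text require observation in the washout year?**

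- Table 1: a year of recorded history and no acid-suppressant prescription in the last year. There is no contact condition.
- Box 2: the same two conditions. The qualifying diagnosis need only precede the index date. Comedication must be recent, a word that Table 1 omits and that the Figure 1 footnote repeats.
- Section 4.6: prescription dates and washout only.
- Sections 4.5 and 4.7.3: continuous observation in Germany ends follow-up only.
- Section 4.7.4: the per-protocol analysis and the censoring adjustment leave the baseline conditions unchanged, so neither tests the look-back.

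As written, then, a German man with an old diagnosis and no visit in the washout year meets the rule. An initiator at least has a prescription at the practice on the index date. A non-initiator's date comes from another man's prescription, and no contact near it is asked for.

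**Size.** The protocol gives no misclassification share, event rate or target HR, so it offers no figure to reproduce. The shares (10, 20, 30%) and true HRs (1.5 and 2) below are assumptions, with a rare outcome over one year. Let h be the true HR against no treatment.

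*Case 1: only initiators are affected.* A share q are continuing users with no excess risk. HR seen = (1 − q)h + q.

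- h = 1.5: 0.9 × 1.5 + 0.1 = 1.45; 0.8 × 1.5 + 0.2 = 1.40; 0.7 × 1.5 + 0.3 = 1.35.
- h = 2: 1.90, 1.80, 1.70.

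*Case 2: only Cohort 6 is affected.* A share c is treated elsewhere and carries the full risk. HR seen = h / [(1 − c) + c·h].

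- h = 1.5: 1.5/1.05 = 1.43; 1.5/1.10 = 1.36; 1.5/1.15 = 1.30.
- h = 2: 2/1.1 = 1.82; 2/1.2 = 1.67; 2/1.3 = 1.54.

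*Case 3: active comparator.* Both drugs have h = 1.5, so the true ratio is 1. Continuing users carry no excess risk, with shares q1 (target) and q2 (comparator). HR seen = [(1 − q1)1.5 + q1] / [(1 − q2)1.5 + q2].

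- Equal shares: 1.00.
- 30% against 10%: 1.35/1.45 = 0.93.
- 10% against 30%: 1.45/1.35 = 1.07.

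*Case 4: outcome capture.* True HR is 1, and outcomes in non-initiators are captured at a fraction s of the rate in initiators. HR seen = 1/s.

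- s = 0.9, 0.8, 0.7: 1.11, 1.25, 1.43.

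Against non-initiators, exposure error pulls toward 1 and poorer outcome capture can push above 1. Against active comparators, the direction depends on which arm holds more continuing users.

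**The case against.** The protocol is open about most of this. Section 4.9 concedes fragmented German histories, section 4.6 says first use cannot be identified with certainty, and Box 1 and section 4.9 accept that Cohort 6 may hold over-the-counter users. Earlier acid-suppressant use, beyond 12 months, is a covariate. That stands: nothing is concealed. But the covariate comes from the same incomplete records, and the over-the-counter discussion rests on episodic use, which does not carry over to prescriptions from another practice.

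Men who qualify through comedication should have a recent record, given the wording of Box 2. That also stands, and it confines the empty-year problem mainly to the diagnosis route. It would be too much to say that one old visit admits any German man.

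Figure 1, which is said to hold the assessment windows, and the German part of Annex 1 are not in the text available here. Either could carry an observation rule. If so, Table 1 and Box 2 should repeat it.

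Three stronger readings are tempting and not supported:

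- **That section 4.9 claims the errors cancel, or that a null result is reassuring.** It says only that both groups are affected, which is true. The weakness is that it gives no direction and no check.
- **That every German HR moves toward 1.** Cases 3 and 4 show otherwise.
- **That the attenuations in cases 1 and 2 can be combined.** That would give continuing users no excess risk among initiators and full excess risk in Cohort 6. Nothing in the protocol justifies both assumptions at once.

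**Conclusion.** The point holds for DA Germany. The visible eligibility text does not require a man to have been observed in the year on which his status as initiator or non-initiator depends, and the protocol's own account of German care makes an empty year weak evidence. That both groups are affected is no protection, because the error is of a different kind in each arm.

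The size cannot be derived from the document. Under assumed shares of 10 to 30%, a true HR of 1.5 against non-initiators falls to between 1.45 and 1.35 in case 1, or between 1.43 and 1.30 in case 2. These are alternatives and are not to be added. For active comparators no general direction can be stated. The change is worth making before analysis, but it reduces the problem without removing it.

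**What to change.** 1. In Table 1 and Box 2, add for DA Germany, in every cohort: at least one recorded contact or prescription of any drug at the practice in the 365 days before the index date, not counting the index day, in addition to at least one year since the first record.

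2. Replace the last sentence of the German paragraph in section 4.9 with directions by contrast, for example: *Against non-initiators, unrecorded treatment moves the HR toward 1, while poorer outcome capture in non-initiators can move it above 1. Against active comparators, the direction depends on the relative shares of continuing users.*

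The cost is one eligibility line and a short rewrite. Infrequent attenders are lost from the German cohorts. The rule removes men with an unobserved year but cannot detect prescribing at another, unlinked practice, so section 4.9 should keep that as a stated limitation.
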